5.8.3.2.2 Management of Hypertension

For subjects experiencing an increase in systolic and/or diastolic blood pressure that is persistent and may be associated with the study treatment, recommendations for the clinical management of hypertension are described below in [Table 7](#).

Table 7 Management and Dose Modification Guidelines for Hypertension

Hypertension	Action and Dose Modification
(Scenario A) 
 • Asymptomatic and persistent^a SBP of ≥ 140 and < 160 mmHg, or DBP ≥ 90 and < 100 mmHg, or 
 • Clinically significant increase in DBP of 20 mmHg (but still below 100 mmHg). 	
 • Continue study treatment at the current dose • Adjust current or initiate new antihypertensive medication • Titrate antihypertensive medication(s) during the next 2 weeks as indicated to achieve well-controlled^b BP • If BP is not well controlled within 2 weeks, consider referral to a specialist and go to scenario (B).
(Scenario B) 
 • Asymptomatic SBP ≥ 160 mmHg, or DBP ≥ 100 mmHg, or 
 • Failure to achieve well-controlled BP within 2 weeks in Scenario A 	
 • Interrupt study treatment if clinically indicated • Adjust current or initiate new antihypertensive medication(s) • Titrate antihypertensive medication(s) during the next 2 weeks as indicated to achieve well-controlled BP • Once BP is well controlled^b, restart study treatment reduced by one dose level
or 
 • Symptomatic^c hypertension • Persistent SBP ≥ 160 mmHg, or DBP ≥ 100 mmHg, despite antihypertensive medication and dose reduction of study treatment 	
 • Interrupt study treatment • Adjust current or initiate new antihypertensive medication(s) • Titrate antihypertensive medication during the next 2 weeks as indicated to achieve well-controlled BP • Referral to a specialist for further evaluation and follow-up is recommended • Once BP is well controlled, restart study treatment reduced by one dose level
Refractory hypertension unresponsive to above interventions or hypertensive crisis.	
 • Permanently discontinue study treatment • Continue follow-up per protocol.

BP = blood pressure; DBP = diastolic blood pressure; mmHg = millimetres mercury; SBP = systolic blood pressure;

- a. Hypertension detected in two separate readings during up to three consecutive visits
- b. Well-controlled blood pressure defined as SBP ≤ 140 mm Hg and DBP ≤ 90 mm Hg in two separate readings during up to three consecutive visits.
- c. Symptomatic hypertension defined as hypertension aggravated by symptoms (e.g., headache, light-headedness, vertigo, tinnitus, episodes of fainting) that resolve after the blood pressure is controlled within the normal range.

5.8.3.3 QT Prolongation

Guidelines for dose modification and stopping criteria due to QTc-prolongation are provided in [Table 8](#).

Table 8 Withholding and Stopping Criteria for QTc-Prolongation

QTc-Prolongation ^a	Action and Dose Modification

 • QTc ≥501 msec 	
 • Interrupt study treatment until QTc prolongation resolves to grade 1 or baseline • Test serum potassium, calcium, phosphorus and magnesium. If abnormal correct per routine clinical practice to within normal limits. • Review concomitant medication usage for agents that prolong QTc. • If event resolves, restart study treatment at current dose level^b • If event does not resolve, permanently discontinue study treatments. Consider evaluation with cardiologist. • If event recurs, permanently discontinue study treatments. Consider evaluation with cardiologist.

Abbreviations: msec = milliseconds; QTc = QT interval on electrocardiogram corrected

- Based on average QTc value of triplicate ECGs. For example, if an ECG demonstrates a prolonged QT interval, obtain two or more ECGs over a brief period, and then use the averaged QTc values of the three ECGs to determine if study treatments should be interrupted or discontinued.
- If the QTc prolongation resolves to grade 1 or baseline, the subject may resume study treatment if the investigator and Novartis Medical Lead agree that the subject will benefit from further treatment.

5.8.4 Guidelines for Skin-related Adverse Events

Cutaneous adverse events have been observed in subjects receiving dabrafenib, trametinib or both therapies in combination (see the Investigator Brochures for more information). Recommendations for supportive care and guidelines for dose modifications are provided (Section 5.8.4.1, Section 5.8.4.2, Section 5.8.4.3 and Section 5.8.4.4). The institutional standards for the management of skin-related AEs can differ from these guidelines. In this case, best clinical judgment should be applied and a consultation with the Novartis Medical Lead may be required. In addition, the Sponsor may require biopsies of any new skin lesions especially those suspicious of cuSCC for further study.

5.8.4.1 Rash

Rash is a frequent AE observed in subjects receiving trametinib, dabrafenib, or the combination of both therapies. Guidelines for rash management are based on experience with other MEK inhibitors and EGFR inhibitors [Balagula Y 2010; Lacouture ME 2008] and are provided below (Table 9 and Table 10).

Table 9 Guidelines for Supportive Care of Rash

Type of Care	Action
Prevention/Prophylaxis Start from Day 1 ^a	
 • Avoid unnecessary exposure to sunlight • Apply broad-spectrum sunscreen (containing titanium dioxide or zinc oxide) with a skin protection factor (SPF) ≥ 15 at least twice daily. • Use thick, alcohol-free emollient cream (e.g., glycerine and cetomacrogol cream) on dry areas of the body at least twice daily.
Prevention/Prophylaxis Start from Day 29 and implement for a total of 6 weeks	
 • Topical steroids and antibiotics should be applied at least twice daily starting on Day 29 of study treatment, to body areas such as face, chest, and upper back. 
 ○ Use mild-strength topical steroid (hydrocortisone 1% cream) or 
 ○ topical antibiotic (e.g., clindamycin) or oral antibiotics (e.g., doxycycline 100 mg BID, minocycline 100 mg BID)
Symptomatic Care	
 • Pruritic lesions: cool compresses and oral antihistamine therapies • Fissuring lesions: Monsel's solution, silver nitrate, or zinc oxide cream • Desquamation: thick emollients and mild soap • Paronychia: antiseptic bath, local potent corticosteroids in addition to oral antibiotics; if no improvement, consult dermatologist or surgeon • Infected lesions: appropriate bacterial/fungal culture-driven systemic or topical antibiotics

BID = twice daily; SPF = skin protection factor

a. Subjects who develop rash/skin toxicities should be seen by a qualified physician and should receive evaluation for symptomatic/supportive care management

Guidelines for management and dose reduction for rash considered to be related to study treatment are provided in [Table 10](#).

Table 10 Management and Dose Modification Guidelines for Rash

CTCAE Grade	Adverse Event Management	Action and Dose Modification
Grade 1	
 Initiate prophylactic and symptomatic treatment measures Use moderate strength topical steroid^a Reassess after 2 weeks 	
 Continue study treatment If rash does not recover to baseline within 2 weeks despite best supportive care, reduce study treatment by one dose level^b
Grade 2	
 Initiate prophylactic and symptomatic treatment measures Use moderate strength topical steroid^a Reassess after 2 weeks 	
 Reduce study treatment by one dose level 
 If rash recovers to ≤grade 1 within 2 weeks, increase dose to previous dose level If no recovery to ≤grade 1 within 2 weeks, interrupt study treatment until recovery to ≤grade 1 Restart study treatment at reduced dose level^b
Grade ≥3	
 Use moderate strength topical steroids^a PLUS oral methyl-prednisolone dose pack Consult dermatologist 	
 Interrupt study treatment until rash recovers to grade ≤1 Restart^b with study treatment reduced by one dose level^c If no recovery to grade ≤2 within 4 weeks, permanently discontinue study treatment

CTCAE = Common Terminology Criteria for Adverse Events

a. Moderate-strength topical steroids: hydrocortisone 2.5% cream or fluticasone propionate 0.5% cream

b. Approval of Novartis Medical Lead is required to restart study treatment after >21 days of interruption.

c. Escalation of study treatment to previous dose level may be considered if no rash is evident 4 weeks after restarting study treatment

5.8.4.2 Severe Cutaneous Adverse Reactions (SCARs)

Cases of SCARs, including Stevens-Johnson syndrome, and drug reaction with eosinophilia and systemic symptoms (DRESS), which can be life-threatening or fatal, have been reported during treatment with dabrafenib in combination with trametinib. Before initiating treatment, patients should be advised of the signs and symptoms and monitored closely for skin reactions. If signs and symptoms suggestive of SCARs appear, dabrafenib and trametinib should be permanently discontinued.

5.8.4.3 Guidelines for Hand-foot Skin Reactions (HFSR)

Episodes of Hand-foot Skin Reaction (HFSR) have been observed in subjects receiving dabrafenib. Guidelines for management of HFSR are based on experience with other kinase inhibitors [Lacouture ME 2008; McLellan B 2011] and are listed Table 11.

Table 11 Management and Dose modification Guidelines for Hand-Foot Skin Reaction (HFSR)

CTCAE Grade	Adverse Event Management	Action and Dose Modification
Grade 1 ^a	
 Life style changes recommended^b Initiate symptomatic treatment^c if clinically appropriate 	
 Continue study treatment at current dose level
Grade 2	
 Life style changes recommended^b Initiate symptomatic treatment^c 	
 Interrupt study treatment until recovery to ≤grade 1^d Recovery to ≤grade 1 within 7 days: Restart study treatment at previous dose level No recovery to grade ≤1 within 7 days or ≥ 2nd occurrence: restart with study treatment reduced by one dose level^e
Grade ≥3	
 Life style changes recommended^b Initiate symptomatic treatment^c Consult dermatologist 	
 Interrupt study treatment until recovery to ≤ grade 1^d Restart with study treatment reduced by one dose level^e If 3rd occurrence, discontinue study treatment permanently

CTCAE = Common Terminology Criteria for Adverse Events

- A full-body skin examination and a removal of pre-existing calluses and keratotic skin is recommended prior to initiation of study treatment
- Life-style changes: (1) reduce exposure of hands and feet to hot water, (2) avoid traumatic activity including vigorous exercise especially in the first 4 weeks after start of study treatment, (3) avoid constrictive footwear, (4) avoid excessive friction on the skin, when applying topical treatments, (5) wear thick cotton socks and gloves, and shoes with padded insoles
- Symptomatic Treatments: (1) use moisturizing creams frequently and especially on hands and feet (2) consider topical keratolytics: urea 20-40 % cream, or salicylic acid 6%, or tazarotene 0.1% cream, or fluorouracil 5% cream; (3) erythematous areas: clobetasol propionate 0.05% ointment; (4) Pain: topical lidocaine 2%, and / or systemic pain medication such as nonsteroidal anti-inflammatory drugs, codeine, and pregabalin
- Approval of Novartis Medical Lead is required to re-start study treatment after ≥21 days of interruption.
- Escalation of study treatment to the previous dose level is allowed if no HFSR is observed in the 4 weeks subsequent to dose reduction.

5.8.4.4 Guidelines for cuSCC

Cutaneous squamous cell carcinomas have been observed in subjects treated with dabrafenib and the combination of dabrafenib and trametinib (see dabrafenib and trametinib combination IB). These treatment-related cuSCC should be surgically removed according to institutional practice. Dose modifications or interruptions of the study treatment are not required for cuSCC. Occurrence of cuSCC must be reported as an SAE. Submit cuSCC tumor tissue for analysis as directed in the SPM.

5.8.5 Guidelines for Other Adverse Events of Special Interest

5.8.5.1 Guidelines for Pyrexia

Episodes of pyrexia have been observed in subjects receiving dabrafenib monotherapy, and is increased in incidence and severity in subjects receiving dabrafenib in combination with trametinib. In a minority of cases the pyrexia was accompanied by symptoms such as severe chills, dehydration, hypotension, dizziness or weakness.

Subjects should be instructed on the importance of immediately reporting febrile episodes. In the event of a fever, the subject should be instructed to take non-steroidal anti-pyretics (e.g. - ibuprofen or acetaminophen/paracetamol) as appropriate to control fever. The use of oral corticosteroids should be considered in those instances in which anti-pyretics are insufficient. Monitor serum creatinine and other evidence of renal function during and following severe events of pyrexia (see Section 5.8.5.3).

Guidelines regarding management and dose reduction for pyrexia considered to be related to study treatment are provided in [Table 12](#).

Table 12 Management and Dose Modification Guidelines for Pyrexia

Adverse Event	Adverse Event Management	Action and Dose Modification
Pyrexia ^a	
All Events:
 
 • Clinical evaluation for infection and hypersensitivity^c • Laboratory work-up^c • Hydration as required^d 
1st Event:^b
 
 • Administer anti-pyretic treatment as clinically indicated and initiate prophylactic treatment if associated with rigors, renal failure, dehydration or hypotension^e 
2nd Event^f
 
 • Within 3 days of onset of pyrexia 
 ○ Optimize anti-pyretic therapy ○ Consider oral corticosteroids (i.e., prednisone 10 mg) for at least 5 days or as clinically indicated^f 
Subsequent Events:
 
 • Within 3 days of onset of pyrexia: 
 ○ Optimize oral corticosteroid dose as clinically indicated for recalcitrant pyrexia^f ○ If corticosteroids have been tapered and pyrexia recurs, restart steroids ○ If corticosteroids cannot be tapered consult Novartis Medical Lead 	
1st Event:
 
 • Interrupt dabrafenib • Continue trametinib • Once pyrexia resolves to baseline, restart dabrafenib at the same dose level 
 ○ If fever was associated with rigors, renal failure, dehydration or hypotension, reduce dabrafenib by one dose level^g 
2nd Event:
 
 • Interrupt dabrafenib • Continue trametinib • Once pyrexia resolves to baseline, restart dabrafenib at the same dose level 
 ○ If fever was associated with rigors, renal failure, dehydration or hypotension, reduce dabrafenib by one dose level^g 
Subsequent Events:
 
 • Interrupt dabrafenib • Continue trametinib • Once pyrexia resolves to baseline, restart dabrafenib reduced by one dose level^g • If dabrafenib must be reduced to <75 mg BID, permanently discontinue dabrafenib. Trametinib may be continued

Table 12 Management and Dose Modification Guidelines for Pyrexia (Continued)

- a. Pyrexia is defined as a body temperature equal to or above 38.5 Celsius or 101.3° Fahrenheit.
- b. For subjects experiencing pyrexia, a clinical evaluation and laboratory work-up is mandatory for each event; anti-pyretic treatment should be started immediately at the first occurrence and prophylactic anti-pyretic treatment is recommended
- c. Thorough clinical examination for signs and symptoms of infection or hypersensitivity is required; laboratory work-up should include full-blood-count, electrolytes, creatinine, blood urea nitrogen (BUN), C-reactive protein (CRP), liver-function tests, blood culture, and urine culture.
- d. Oral hydration should be encouraged in subjects without evidence of dehydration. Intravenous hydration is recommended in subjects experiencing pyrexia complicated by dehydration/hypotension.
- e. Anti-pyretic treatment may include acetaminophen, ibuprofen, or suitable anti-pyretic medication according to institutional standards. Prophylactic anti-pyretic treatment may be discontinued after three days in the absence of pyrexia
- f. In subject experiencing pyrexia complicated by rigors, severe chills, etc., which cannot be controlled with anti-pyretic medication, oral corticosteroids should be started at the 2nd event and doses should be gradually increased for subsequent events.
- g. Dabrafenib should be reduced by one dose level after three episodes of pyrexia complicated by rigors, severe chills, etc., which cannot be managed by best supportive care and increasing doses of oral steroids. Escalation of dabrafenib is allowed if no episode of pyrexia is observed in the 4 weeks subsequent to dose reduction.

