1.2.3 BRAF and MEK Inhibitors as Combination Therapy

Clinical evaluation of the dabrafenib 150 mg BID + trametinib 2 mg QD (150/2) combination treatment has shown efficacy in patients with V600 mutant melanoma. The results of the randomized Part C of Study BRF113220 in BRAF-inhibitor naïve subjects demonstrated an improved efficacy profile for the 150/2 combination treatment compared to dabrafenib monotherapy across all efficacy parameters tested.

BRF113220 was a Phase I/II study with 4 parts that include a randomized part (Part C) which investigated the clinical activity, durability of response, safety/tolerability and population PK parameters in the three different arms in subjects with BRAF-mutant melanoma ($n = 162$). In Part C, a statistically significant ($p = 0.0264$) increase in the confirmed overall response rate was observed in the 150/2 treatment arm (76%) when compared to the dabrafenib monotherapy arm (54%) [Flaherty KT 2012b]. Moreover, the rate of complete responses was higher in the 150/2-treatment arm (9% vs 4%) while early disease progression (i.e., no best response of disease progression (PD) at the first timepoint assessment), was absent (0 vs 6%) when compared to the dabrafenib monotherapy arm. Clinically more important, the investigator-assessed PFS was significantly prolonged for the 150/2 combination arm relative to the dabrafenib monotherapy arm ($HR = 0.39$; $p < 0.0001$) [Flaherty KT 2012b]. This benefit was sustained at 12 months, with a 12-month progression-free rate of 41% in the 150/2 arm vs 9% in the dabrafenib monotherapy arm. While a significant difference in PFS was also observed in the 150/1 combination therapy group compared to dabrafenib monotherapy ($HR = 0.56$, $p = 0.0057$), the benefit was lower at 12 months (12-month progression-free rate of 26%) [Flaherty KT 2012b].

Safety data reported from Part C showed that dose-limiting toxic effects were infrequently observed in subjects receiving combination therapy with 150 mg of dabrafenib and 2 mg of trametinib (combination 150/2). Cutaneous squamous-cell carcinoma was seen in 7% of subjects receiving combination 150/2 and in 19% receiving dabrafenib monotherapy ($p = 0.09$), whereas pyrexia was more common in the combination 150/2 group than in the monotherapy group (71% vs. 26%) [Flaherty KT 2012b].

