MEK115306 study is a double blind randomized phase III study that recruited 423 previously untreated metastatic melanoma patients who had BRF V600E or V600K mutation. Eligible patients were randomized to receive dabrafenib 150mg bid plus trametinib 2mg qd, or dabrafenib 150mg bid plus placebo. The primary endpoint was PFS. The results showed the combination significantly improved PFS (median PFS: 9.3 vs 8.8 months, HR=0.75, $p=0.03$) and response rate (67% vs 51%, $p=0.0002$). The interim OS analysis at 6 months showed the survival rate was 93% and 85% in the combination arm vs dabrafenib arm (HR=0.63, $p=0.02$). However, a pre-defined specific efficacy stopping boundary of OS (two-side $p=0.00028$) was crossed. So the survival follow-up is still on-going as of December 2014.

In this study, 9% patient from combination treatment arm and 5% from dabrafenib monotherapy arm permanently discontinued study medication before disease progression. In addition, dose reduction was required in 25% and 13% of patients receiving combination and dabrafenib monotherapy, respectively.

The adverse event profile of combination treatment was different from dabrafenib monotherapy. The patients who received combined treatment experienced more frequent pyrexia(51% vs 28%), chill(30% vs 16%), diarrhea(24% vs 14%), hypertension(22% vs 14%), vomiting(20% vs 14%), peripheral edema(14% vs 5%), elevated ALT (11% vs 5%) or AST (11% vs 3%), decreased left ventricular ejection fraction(LVEF)(4% vs 2%), dermatitis acneiform(8% vs 3%), but less frequent cutaneous squamous-cell carcinoma(2% vs 9%), hyperkeratosis(3% vs 32%), skin papilloma(1% vs 21%), hand-foot syndrome(5% vs 27%), dry skin(9% vs 13%), pruritus(8% vs 12%) and alopecia(7% vs 26%). [Long GV 2014]

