5.8.1 Dose Levels of dabrafenib and trametinib

The dose levels for this study are provided in [Table 4](#).

Table 4 Dose Level Reduction Guidelines

Dose Level	Dabrafenib Dose/Schedule	Trametinib Dose/Schedule
Starting Dose	150 mg BID	2 mg once daily
-1 (1 st Dose reduction)	100 mg BID	1.5 mg once daily
-2 (2 nd Dose reduction)	75 mg BID	1.0 mg once daily

Abbreviation: BID = twice daily

Re-escalation of dose levels is permitted if an AE resolves to grade 1 or baseline at the reduced dose level, and no additional toxicities are seen after 4 weeks of study treatment at the reduced dose.

A dose reduction below 75 mg BID for dabrafenib or below 1 mg once daily for trametinib is not allowed. If a dose reduction below 75 mg BID for dabrafenib is required, dabrafenib will be permanently discontinued but these subjects will be allowed to continue trametinib.

If a dose reduction below 1.0 mg once daily for trametinib is required, then trametinib will be permanently discontinued, but these subjects will be allowed to continue dabrafenib.

Note: Approval from the Novartis Medical Lead is required to restart study treatment after ≥21 days of interruption. Study drug must be discontinued permanently if any interruption goes beyond 26 weeks.

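### Table 12 reduces dabrafenib after a complicated first or second fever, but footnote g on those lines sets a trigger that neither event can meet

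*Protocol*

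**What the plan says.** Protocol 5.8.5.1, Table 12, gives separate restart instructions for the first, second and subsequent pyrexia events. The first- and second-event cells carry the same conditional line: "If fever was associated with rigors, renal failure, dehydration or hypotension, reduce dabrafenib by one dose level". The subsequent-events cell has no such condition: "Once pyrexia resolves to baseline, restart dabrafenib reduced by one dose level". All three reduction lines are marked with footnote g.

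Footnote g has two sentences. The first says when dabrafenib should come down by one step: "after three episodes of pyrexia complicated by rigors, severe chills, etc., which cannot be managed by best supportive care and increasing doses of oral steroids". The second is a re-escalation rule: "Escalation of dabrafenib is allowed if no episode of pyrexia is observed in the 4 weeks subsequent to dose reduction".

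Footnote f covers complicated fevers that antipyretics do not control. It starts oral steroids at the second event and raises the dose at later ones.

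Table 4 in Section 5.8.1 sets the dabrafenib levels at 150, 100 and 75 mg BID, and the text below it fixes the floor: "A dose reduction below 75 mg BID for dabrafenib or below 1 mg once daily for trametinib is not allowed".

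**The concern.** The body of the table and the footnote attached to it give different conditions for the same action. On the table body, one complicated fever is enough. On the footnote, three are needed, and steroid escalation must have failed as well. The protocol does not say which governs.

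This is an operative dosing rule for a frequent toxicity of the combination. Section 1.2.3 reports pyrexia in 51% of combination subjects in one phase III trial and 71% in the phase I/II randomised part. Section 1.2.1 describes serious cases on dabrafenib with severe rigors and, in some, dehydration or hypotension. A site that took the footnote as the rule would return such a subject to full-dose dabrafenib. Two sites could treat the same event differently. The SAP's counts of dose reductions (2.4.1.4) and its relative dose intensity, RDI (2.4.1.3), would then mix two rules.

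**Working it through.** **Can a first or second event meet footnote g?** No, on two grounds.
- The episode count is 1 or 2, and the footnote asks for three.
- Under footnote f, steroids start at the second event and are raised only afterwards, so increasing doses cannot yet have failed.

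**Does footnote g fit its third anchor?** Not exactly. The subsequent-events line reduces after any further fever, complicated or not. A third, complicated, steroid-refractory fever already falls inside that line, so there the footnote either narrows the rule or adds nothing.

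**What do comparable footnotes do?** The markers on the reduction lines for rash (Table 10, note c), hand-foot reaction (Table 11, note e) and diarrhea (Table 13, note d) carry only a re-escalation rule. Footnote g alone restates a reduction trigger.

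**Tracing the two readings.** Assume a start at 150 mg BID, three consecutive complicated fevers and no re-escalation between them.

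| After fever | Table body | Footnote g as trigger |
|---|---|---|
| 1st | 100 mg BID (200 mg/day) | 150 mg BID (300 mg/day) |
| 2nd | 75 mg BID (150 mg/day) | 150 mg BID (300 mg/day) |
| 3rd | dabrafenib stopped (next step is below the floor) | at the earliest 100 mg BID (200 mg/day) |

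After one complicated fever the daily doses differ by 300 − 200 = 100 mg, one third of the starting dose.

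**Illustration for RDI.** The plan gives no figure to reproduce. Inputs:
- The planned dose is 300 mg/day over whole exposure (SAP 2.4.1.3, worked example).
- A month is 30.4375 days (SAP 2.1.3.4).
- Exposure lengths are assumed, at the boundaries of the bands in SAP 2.4.1.1.
- The two paths differ for 28 days, the fever-free period that footnote g requires before re-escalation. Dosing is assumed uninterrupted on each path for those days and identical otherwise.

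Dose difference = (300 − 200) × 28 = 2,800 mg. RDI difference = 2,800 / (300 × D), with D the exposure in days:

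| Exposure | D (days) | RDI difference (percentage points) |
|---|---|---|
| 3 months | 91.3 | 10.2 |
| 6 months | 182.6 | 5.1 |
| 12 months | 365.25 | 2.6 |
| 24 months | 730.5 | 1.3 |
| 36 months | 1,095.8 | 0.9 |

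**Projected number with any pyrexia.** At the cited rates, 0.51 × 65 = 33.2 and 0.71 × 65 = 46.2, so about 33 to 46 of 65 subjects. Complicated fever is a smaller group, since Section 5.8.5.1 says "In a minority of cases the pyrexia was accompanied by symptoms such as severe chills". The documents do not give its size.

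**The case against.** The best defence is that footnote g is additive. It does not say that reduction happens only after three episodes, and a reading that lets a footnote cancel the two lines it annotates would make those lines void. The neighbouring tables support a benign explanation: g may sit on all three lines for the sake of its re-escalation sentence, as the markers in Tables 10, 11 and 13 do.

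Much of this stands. A careful investigator would probably follow the table body. But the protocol does not say the footnote is additive, and on that reading its first sentence is redundant. The sentence therefore either conflicts with the table or does no work, and deleting it is right in both cases. The pattern in the sister tables supports that deletion.

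It is also fair to object that the study is over. Last visit was 19-Apr-2021 (SAP 2.1.1), so new wording cannot alter a dose in this trial. That limits the value of the change but does not remove the inconsistency.

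**Conclusion.** The inconsistency is real and is in current protocol text. The first- and second-event lines reduce on the complication alone, while the footnote marked on them states a condition that cannot hold at either event. After one complicated fever from the starting dose, the readings give 200 and 300 mg/day. The consequence is for patient safety and dosing consistency, and through them for the descriptive dose-reduction and RDI summaries.

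Four stronger conclusions might be inferred, and the documents do not support them.
- **That subjects were misdosed.** Nothing in either document shows which trigger sites followed.
- **That the primary result is compromised.** The definition and analysis method of ORR do not depend on this rule.
- **That the RDI differences are minimums.** Table 12 interrupts dabrafenib at every further fever, so recurrence on the full-dose path would shrink the gap, while staying longer at the reduced dose would widen it. Whether any subject would change RDI category cannot be said without individual exposure data.
- **That 33 to 46 of 65 is a ceiling.** It is a projection of any pyrexia from earlier trials. Section 1.2.3.1 says combination exposure tended to be higher in Japanese patients, so the rate here could differ. The number of subjects affected is unknown.

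**What to change.** Delete the first sentence of footnote g, the one with the three-episode trigger. Keep its re-escalation sentence on all three reduction lines and let the triggers in the body of Table 12 govern. If the additive reading was intended, the deletion changes nothing. The cost is one sentence of wording, with no procedures or data. For this completed study, the benefit is a clear rule against which to read the dose summaries, and wording that is safe to reuse elsewhere.

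If the sponsor wants to know which trigger was followed, the SAP already plans listings of doses with change reasons (2.4.1.2) and of all adverse events (2.8.1), which could be matched by date. The SAP's dosing examples record the reason only as an adverse event, so the match would be needed. Mainland Chinese data from 01-Jul-2019 onwards cannot be used (2.1.1). This check is optional and would change no planned result.
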